13. SAFETY ANALYSES

All safety analyses will be based on the Safety Population.

A listing of all deaths will be presented.

13.1 Adverse Events

All AE summaries will be restricted to treatment-emergent AEs (TEAEs), which are defined as those AEs that occurred any time on or after the first in-clinical application of study drug through the last application of study medication and those existing AEs that worsened during this same period. If it cannot be determined whether the AE is treatment emergent due to a partial onset date, then it will be counted as such; see [Appendix B](#) for the imputation of missing dates algorithm. Verbatim terms in the eCRFs will be mapped to preferred terms and system organ classes using the MedDRA Version 22.0.

Each AE summary will be displayed by treatment group. Summaries that are displayed by system organ classes and preferred terms will be ordered by descending order of incidence of system organ class and preferred term within each system organ class. Summaries of the following types will be presented:

- Overall summary of TEAEs that contain an overview of each item below.
- Subject incidence of TEAEs and total number of unique TEAEs by MedDRA system organ class and preferred term.
- Subject incidence of TEAEs by MedDRA system organ class, preferred term, and maximum severity. At each level of subject summarization, a subject is classified according to the maximum severity if the subject reported 1 or more events. Adverse events with missing severity will be considered severe for this summary.

- Subject incidence of TEAEs by MedDRA system organ class, preferred term, and closest relationship to study drug (Related/Not Related). Related AEs are those reported as “Definite,” “Probable,” or “Possible,” and unrelated AEs are those reported as “Unlikely” or “Unrelated.” At each level of subject summarization, a subject is classified according to the closest relationship if the subject reported 1 or more events. Adverse events with a missing relationship will be considered related for this summary.
- Subject incidence of serious TEAEs and total number of unique serious TEAEs by MedDRA system organ class and preferred term.
- Subject incidence of TEAEs leading to study drug discontinuation by MedDRA system organ class and preferred term.
- Subject incidence of TEAEs leading to death as an outcome by MedDRA system organ class and preferred term.

Separate listings of all AEs, all SAEs and all AEs leading to study drug discontinuation will be provided.

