9 ADVERSE EVENTS

Adverse events will be assessed and collected after the initiation of study drug treatment through the end of the subject's last visit. In order to avoid bias in eliciting AEs, subjects/caregivers should be asked the following non-leading question: "*How have you felt since your last visit?*" Adverse events will be assessed and reported after the subject is dosed, beginning from Baseline through the end of the subject's last visit. SAEs will be collected from the time of consent through the end of the subject's last visit. Adverse events that occur from time of consent up to the time of treatment administration should be recorded as medical history for all participants. Treatment-related

adverse events will be followed up until resolution or up to one year after last treatment, whichever occurs earlier.

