12.1.3 Analysis of Safety

12.1.3.1 Adverse Events

All AEs that occur during the study will be recorded and classified on the basis of Medical Dictionary for Regulatory Activities (MedDRA) terminology. Treatment-emergent AEs (TEAEs) are defined as AEs that occurred any time on or after the first in-clinic application of study drug through the last application of study medication. Medical history noted prior to the first study drug administration that worsen after Baseline will also be reported as AEs and included in the summaries.

Treatment-emergent AEs will be summarized by treatment group, the number of subjects reporting a TEAE, System Organ Class (SOC), preferred term, severity, relationship to study drug (causality), and seriousness. When summarizing AEs by severity and relationship, each subject will be counted only once within a system organ class or a preferred term by using the event with the highest severity and greatest relationship within each classification.

Serious AEs will be summarized by treatment group, severity, and relationship to study drug, and individual SAEs will be listed by subject. In addition, a list of subjects who prematurely discontinue from the study due to an AE will be provided.

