The study treatment period is defined from randomization through completion of Week 12/ET1 visit and the safety follow-up period is from the completion of Week 12 through the completion of Week 24/ET2 visit.

After all subjects have completed their Week 12/ET1 visit, thus completing the Treatment Period of the study, the database through Week 12/ET1 will be frozen and unblinded for purposes of the primary analysis of efficacy and safety. While this analysis is being prepared, the subjects will continue through Week 24/ET2. After all subjects have completed their Week 24/ET2 visit, the database will be locked and the follow-up data will be analyzed.

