14. CHANGES TO PROTOCOL-SPECIFIED ANALYSES

The following modifications and/or clarifications to the methodology specified in the protocol will be:

- The DLQI and CDLQI will be summarized separately
- The order of the exploratory endpoints was updated
- The Mean percent change in baseline endpoint was updated to be more generic in order to analyze the median in the case of skewness
- Proportion of subjects with 90% and 95% clearance exploratory endpoints were added in order to provide additional clinically meaningful categories for analysis

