14.3.1.3	Summary of Treatment-Emergent Adverse Events by System Organ Class, Preferred Term, and Maximum Severity	Safety
14.3.1.4	Summary of Treatment-Emergent Adverse Events by System Organ Class, Preferred Term, and Relationship to Study Drug	Safety
14.3.1.5	Summary of Serious Treatment-Emergent Adverse Events by System Organ Class and Preferred Term	Safety
14.3.1.6	Summary of Treatment-Emergent Adverse Events Leading to Study Drug Discontinuation by System Organ Class and Preferred Term	Safety

Table Number	Table Title	Analysis Population
14.3.1.7	Summary of Treatment-Emergent Adverse Events Leading to Death by System Organ Class and Preferred Term	Safety
14.3.2	Listings of deaths, other serious and significant adverse events	
14.3.2.1	Listing of Serious Adverse Events	Safety
14.3.2.2	Listing of Adverse Events Leading to Study Drug Discontinuation	Safety
14.3.2.3	Listing of Deaths	Safety
14.3.6	Other safety data	
14.3.6.1.1	Summary of Local Skin Reaction (LSR) Composite Score by Visit	Safety
14.3.6.1.2	Summary of Local Skin Reaction (LSR) Score Results by Visit	Safety
14.3.6.1.3	Shift Summary of Local Skin Reaction (LSR) Score Results by Visit	Safety
14.3.6.2	Summary of Events of Special Interest	Safety
14.3.6.3	Summary of Physical Examination Findings	Safety
14.3.6.4	Summary of Patch Testing Results	Safety

Figure Number	Figure Title	Analysis Population
14.2.1.5	Forest Plot: Odds Ratio (95% CI) of the Proportion of Subjects with Complete Clearance at Week 12	ITT
14.2.3.3.2	Percent Change from Baseline in Lesion Count over Time by Treatment Group	ITT
14.2.3.4.2	Mean Change from Baseline in Lesion Count over Time by Treatment Group	ITT
14.2.3.6.2	Kaplan-Meier Plot of Time to Complete Clearance (Days) from Start of Dosing	ITT
14.2.3.10.2	Plot of Complete Clearance at Week 12 by Highest Dichotomized Categorized BOTE Score	ITT

Section 16.2: List of Data Listings

ICH Listing Number	Listing Title	Analysis Population
16.1.7	Subject Randomization	ITT
16.2	SUBJECT DATA LISTINGS	
16.2.1	Discontinued subjects	
16.2.1.1	Subject disposition	Enrolled
16.2.2	Protocol deviations	
16.2.2.1	Protocol Deviations	ITT
16.2.2.2	Inclusion/Exclusion Criteria	Enrolled
16.2.3	Subjects excluded from the efficacy analysis	
16.2.3.1	Analysis Populations	Enrolled
16.2.4	Demographic data	
16.2.4.1	Demographic and Baseline Characteristics	ITT
16.2.4.2	Patch Testing Consent/Assent	Enrolled
16.2.4.3	Medical History	ITT
16.2.4.4	Prior and Concomitant Medications	ITT

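### AEs with known onset after the last dose reach no by-arm AE table, such recurrence is tabulated only if a lesion count confirms it, and the protocol's SAE breakdown is dropped undeclared

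*Combined protocol and SAP*

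**What the plan says.** **AE tables.** Final SAP section 13.1: "All AE summaries will be restricted to treatment-emergent AEs (TEAEs". The window is "on or after the first in-clinical application of study drug through the last application of study medication", plus existing AEs that worsen in that period. Protocol section 12.1.3.1 uses the same limits: "on or after the first in-clinic application of study drug through the last application of study medication". Under SAP 13.1, an event counts as treatment-emergent if a partial onset date leaves its status undetermined. Separate listings of all AEs, all SAEs and AEs leading to drug discontinuation are planned.

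**Collection.** Protocol section 9: "Adverse events will be assessed and reported after the subject is dosed, beginning from Baseline through the end of the" subject's last visit. SAEs are collected from consent. SAP section 6 defines a safety follow-up period from Week 12 to Week 24/ET2 and says that after the Week 24 visits "the database will be locked and the follow-up data will be analyzed".

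**Recurrence.** Protocol sections 1.2.1 and 4.1 treat a molluscum recurrence as an AE. Sections 6.2.8 and 6.2.9 ask about it at Weeks 16, 20 and 24, the first two expected to be by telephone. The SAP endpoint (section 10.1) requires a lesion count above 0 after a count of 0.

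**SAEs.** Protocol section 12.1.3.1: "Serious AEs will be summarized by treatment group, severity, and relationship to study drug". The only by-arm SAE table in SAP Appendix D is 14.3.1.5, "Summary of Serious Treatment-Emergent Adverse Events by System Organ Class and Preferred Term". SAP section 14 opens "The following modifications and/or clarifications to the methodology specified in the protocol will be" and then lists four items, none of them about AEs or SAEs.

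**The concern.** The trial follows every subject for safety after dosing ends, yet no planned AE or SAE table compares the arms over that time. With 2:1 allocation, raw counts taken from a listing cannot be compared directly; a reader would have to count events by arm and work out the incidence by hand.

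Two further points follow from the same rule. An AE with known onset after the final dose that leads to permanent discontinuation falls outside Table 14.3.1.6. Recurrence after treatment, which bears on how durable clearance is, can fall between two definitions: too late to be a TEAE, and not a counted lesion. Table 14.2.3.5 could then understate recurrence after treatment.

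The SAE point is different in kind. There the protocol names a breakdown, the SAP gives another, and the change is not declared.

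**Working it through.** The point is mainly textual, so the passages are set side by side. The only arithmetic is on visit days.

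**1. Which tables cover onset after the last application.** Appendix D of the final SAP has seven AE tables, 14.3.1.1 to 14.3.1.7. All are titled as treatment-emergent tables, and section 13.1 applies the restriction to every AE summary. Number covering known onset after the last application: 0 of 7. The AE part of the special-interest table (14.3.6.2, section 13.3) is also limited to TEAEs; its local skin reaction and BOTE parts are not. Later events appear in Listings 14.3.2.1 to 14.3.2.3, 16.2.7.1 and 16.2.9.6.

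**2. Calendar time outside those tables.** Target days from the protocol: Week 4 = Day 29, Week 8 = Day 57, Week 12 = Day 85, Week 24 = Day 169. Days from Day 1 to Day 169: 169 − 1 = 168.

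- Dosed to Week 12: 169 − 85 = 84 days; 84/168 = 50%.
- Final stop at Week 8: 169 − 57 = 112 days; 112/168 = 67%. Of these, 85 − 57 = 28 days lie within the SAP's own treatment period.
- Final stop at Week 4: 169 − 29 = 140 days; 140/168 = 83%. Of these, 85 − 29 = 56 days lie within the treatment period.

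**3. Recurrence.** Protocol Table 1, section 6.2.9 and section 7.1.1 schedule no lesion count after Week 12/ET1. Both documents are unclear about Week 24: the protocol synopsis and SAP section 4 say recurrence is assessed at that visit, and both place a counting sentence in the scar paragraph, which covers Week 24. A recurrence reported at Week 16 or 20, with known onset after the last application and no unscheduled count, fails both the count definition and the TEAE definition. It is left to listings such as 16.2.7.1 and 16.2.9.5 (telephone contact).

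To size this under the design rates: 227 × 0.36 = 81.7 active and 113 × 0.18 = 20.3 vehicle subjects clear at Week 12, about 102 in all. The documents give no recurrence rate between Weeks 12 and 24. If 5% to 30% of these subjects recur, that is 102 × 0.05 ≈ 5 to 102 × 0.30 ≈ 31 recurrences. This is an upper bound on the number missing from by-arm tables for that group, since it assumes that onset is known and that no count confirms any of them.

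**4. SAEs.** Breakdowns named in the protocol besides arm: severity and relationship. Breakdowns in SAP 13.1 and the title of Table 14.3.1.5: system organ class and preferred term. Overlap: 0 of 2. Serious TEAEs are included in the all-TEAE severity and relationship tables (14.3.1.3 and 14.3.1.4) but cannot be separated there.

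**The case against.** The strongest reply is that the SAP follows the protocol. The TEAE window is the protocol's own, and for non-serious AEs the protocol promises by-arm summaries of TEAEs only. This stands: the first part is an improvement to the plan, and a reader who infers that the SAP shortened the protocol's window would be wrong. The promise to analyze follow-up data is general and names no AE table.

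It is also true that the events are not lost. Listings are planned; scarring and keloid are tabulated by arm at Week 24, and household spread through Week 24. Local skin reaction scores, which cover the reactions most clearly tied to SB206 in Phase 2, are tabulated at the scheduled visits and in Table 14.3.6.2. The discontinuation point is therefore an edge case: it needs a known onset after the final dose, and the stop itself is still counted by arm in the disposition table (SAP 9.1), though without preferred term.

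On recurrence, a reader might infer that reports at Weeks 16 and 20 can never reach a by-arm table. The documents do not support that. These contacts are only expected to be by telephone, unscheduled visits are allowed for medical reasons, the endpoint accepts a count at any point after clearance, and a recurrence with an undetermined partial onset date counts as a TEAE. A count-based definition is also a defensible choice for an exploratory endpoint.

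On SAEs, all are listed, and Phase 2 had none in 256 subjects (protocol 1.1.4). The table shells are not in the documents, so the content of 14.3.1.5 is read from its title and from SAP 13.1. Whether the protocol meant all SAEs or only treatment-emergent ones is open.

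**Conclusion.** The point holds as a cheap improvement. As written, the plan gives no by-arm AE table for events with known onset after the last application, over 84 calendar days for a subject dosed to Week 12 and longer after an earlier final stop. It provides no by-arm summary of later recurrence that is reported but not counted. The loss of severity and relationship from the SAE summary, undeclared in SAP section 14, is the only clear protocol–SAP conflict, and its effect is likely small.

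Two stronger readings are tempting and not supported. The 50% is not a share of missed events, because the documents give no post-treatment AE rate. Nor do they show that the window under-counts AEs on active treatment because clearers may stop early: they give no stopping rate. Assuming that 25% to 75% of Week 12 clearers stop at Week 8, the mean window is 85 − 28 × 0.36 × f on active and 85 − 28 × 0.18 × f on vehicle, where f is that share. This gives 82.5 to 77.4 days against 83.7 to 81.2 days, a difference of about 1.3 to 3.8 days.

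**What to change.** - Keep the TEAE tables. Add by-arm tables of all AEs, SAEs and related AEs from first application through Week 24/ET2, split into on and off treatment.
- Base the table of AEs leading to drug discontinuation on the action-taken field (protocol 9.1), with no onset cut-off at the last dose.
- Add a by-arm recurrence summary among subjects who reached a count of 0. Include recurrence reported as an AE at Weeks 16, 20 and 24, and show it separately from count-based recurrence.
- Reconcile the protocol and SAP passages on whether lesions are counted at Week 24.
- Restore the SAE summary by severity and relationship, stating whether it covers all SAEs or serious TEAEs only, or declare the change in SAP section 14.

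The cost is SAP wording and a few more tables. Onset date, seriousness, severity, relationship and action taken are already recorded for each AE. No endpoint test or sample size changes. The drawback is that more background AEs are counted in both arms, which the on/off-treatment split keeps visible.

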13.2 Local Skin Reaction

The LSR composite score will be calculated by summing up all the numerical responses (0-4) to each individual parameter for a composite score that ranges between 0 and 24. The change from Baseline of the LSR composite score will be summarized descriptively. A table summarizing each LSR parameter (erythema, flaking/scaling, crusting, swelling, vesiculation/pustulation, and erosion/ulceration) score at each scheduled postbaseline assessment will be presented.

Additionally, a shift table comparing the baseline score for each LSR parameter to each scheduled postbaseline assessment will be presented for the Safety Population.

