Inflammatory reactions around the MC has been associated with imminent resolution of MC (sometimes referred to as “beginning-of-the-end” [“BOTE”] sign). The investigator (or designated evaluator) will assess the presence and overall degree of inflammatory reactions at MC lesions at Baseline (before dosing) and Weeks 2 through 12. In most cases, clinical features can differentiate between BOTE and LSR. BOTE may be associated with itch, but not pain. BOTE is usually asymptomatic, self-limited, and localized to individual MC lesions and does not require discontinuation of study treatment or additional treatment. LSR is generally more diffuse, associated with significant itch or tenderness, may necessitate discontinuation of study treatment, and may need treatment for symptomatic relief (e.g., a topical corticosteroid or topical anesthetic). For very severe LSR, systemic corticosteroids may be considered. Investigators will assess the treatment area at each scheduled visit and use their medical judgement to differentiate between BOTE and LSRs. BOTE Inflammation Score and LSR score will be recorded at each visit. BOTE should not be considered an AE. When LSRs are clinically significant at the application site, the investigator should report the condition as an AE(s).

At Baseline (at least 30 minutes after dosing) and Weeks 2 through 12, the investigators will rate LSRs on individual features including erythema, flaking/scaling, crusting, swelling, vesiculation/pustulation, and erosion/ulceration. At Baseline (pre-dose) and Weeks 2 through 12, the investigators will rate BOTE signs using the BOTE Inflammation Score.

The following tables describe the scoring parameters for the BOTE Inflammation Score and LSR score.

BOTE Inflammation Score

Score	Global Assessment	Description
0	No inflammation	No evidence of local inflammation
1	Mild	Minimal erythema and/or edema
2	Moderate	Definite erythema and/or edema with or without hemorrhagic crusting
3	Severe	Erythema and edema with definite hemorrhagic crusting
4	Very severe	Strong reaction spreading beyond the treated area, bullous reaction, erosions

LSR Score

Score	Erythema	Flaking/ Scaling	Crusting	Swelling	Vesiculation/ Pustulation	Erosion/ Ulceration
0	Not present	Not present	Not present	Not present	Not present	Not present
1	Slightly pink	Mild, limited	Isolated crusting	Minimal, limited	Fine vesicles	Superficial erosion

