7. NOTATION OF TREATMENT GROUPS AND VISITS

Analysis visits

Baseline is defined as the last nonmissing value recorded prior to the first application of study drug. If time is not recorded and the assessment was on the same day as the first application of study drug, then it will be assumed the assessment occurred prior to the application of study drug. The baseline record will have an analysis visit of “Baseline”.

For all evaluations of all parameters, assessments will be analyzed according to the visit at which they occurred (i.e., per the eCRF visit label). In order to account for the fact that the Week 12 and Early Termination visits are collected on the same eCRF in the database, a check against the Study Exit form will be made to determine if the visit is a Week 12 or an Early Termination Visit. If the visit is an Early Termination visit, then the visit will be mapped according to the table below. If there is no corresponding Study Exit form on the same date, then it will be considered a Week 12 visit. If there is no assessment in a given visit, then the following visit windows will be applied to determine if an unscheduled visit may be used:

Visit	Analysis Visit	Target Study Day	Study Day Analysis Window
Week 2 (± 3 days)	Week 2	15	Day 12 to 22
Week 4 (± 5 days)	Week 4	29	Day 23 to 43
Week 8 (± 5 days)	Week 8	57	Day 44 to 71
Week 12 (± 5 days)	Week 12	85	Day 72 to 98

Days are measured from the date of randomization. Study days corresponding to measurements are calculated as:

- Assessment date – date of randomization + 1, if assessment date is on or after the date of randomization.
- Assessment date – date of randomization, if measurement date is before the date of randomization.

In the event of multiple unscheduled records falling in the same analysis window, the assessment which is closest to the target study day will be chosen for analysis.

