10.2 Baseline Values

Unless otherwise noted, baseline is defined as the last nonmissing value recorded prior to the first application of study drug. If time is not recorded and the assessment was on the same day as the first application of study drug, then it will be assumed the assessment occurred prior to the application of study drug. If a subject was randomized but not treated, then baseline is defined as the last nonmissing value on or before the date of randomization.

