13.3 Events of Special Interest

Events of Special Interest will include subjects with any TEAE where the preferred term contains “application site”, subjects with at least 1 post-baseline occurrence of moderate BOTE inflammation score, or subjects with at least 1 post-baseline LSR component score ≥ 1 . A summary including the number and percentage of subjects with at least 1 event of special interest, AEs of interest by MedDRA system organ class and preferred term, at least 1 moderate BOTE inflammation score, and any LSR component score ≥ 1 will be provided for the Safety Population. The analysis will also be repeated with the LSR criteria revised to include any post-baseline LSR component (excluding erythema) score ≥ 1 and erythema score ≥ 2 .

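### SAP 13.2 plans LSR change-from-Baseline and shift tables although no pre-dose LSR is scheduled, so the baseline is either a post-dose score or missing

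*Combined protocol and SAP*

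**What the plan says.** Section references are to the final SAP (the version that cites table shells Version 3.0) and to the protocol.

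- **Planned LSR analyses (SAP 13.2).** For the composite: "The change from Baseline of the LSR composite score will be summarized descriptively". For the six components, "a shift table comparing the baseline score for each LSR parameter to each scheduled postbaseline assessment will be presented". A further table gives component scores at each scheduled postbaseline assessment.
- **Baseline rule (SAP 7 and 10.2).** "Baseline is defined as the last nonmissing value recorded prior to the first application of study drug". For a record from the first dosing day that carries no time, the rule is: "then it will be assumed the assessment occurred prior to the application of study drug". SAP 10.2 opens by allowing exceptions that are noted elsewhere. SAP 7 also assigns assessments to visits by their eCRF label.
- **LSR timing.** SAP 4 states: "At Baseline (at least 30 minutes after dosing) and Weeks 2 through 12, the investigators will rate LSRs on individual features". Protocol 7.2.4 gives the same Day 1 timing. Protocol 6.2.2 puts the LSR at step 12, about half an hour after the first dose at step 11. The LSR row of Protocol Table 1, and its footnote 4, make every LSR post-dose. Protocol 6.2.1 lists six Screening procedures, and LSR is not among them.
- **Contrast.** The BOTE score at Baseline is pre-dose (Protocol 6.2.2, Table 1 footnote 4, SAP 4).
- **Use of the post-baseline label (SAP 13.3).** Events of special interest include "or subjects with at least 1 post-baseline LSR component score" of 1 or more.

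**The concern.** A change from baseline needs a value from before treatment. The protocol collects one for BOTE but not for LSR, and the SAP applies its general baseline rule to LSR without comment. Followed literally, that rule can turn a reaction seen half an hour after the first application into the subject's untreated state.

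Tolerability at the application site is the main safety question for this product. Protocol 1.1.4 reports that, in the Phase 2 molluscum study, the only adverse events clearly associated with SB206 were administration site reactions, and that 6 of 7 treatment discontinuations for adverse events were for application site reactions. The protocol also looks for early reactions deliberately, with the 30-minute LSR and a Day 2 telephone call. A baseline rule that subtracts the first reaction from all later ones works against that purpose.

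**Working it through.** The plan gives no figure to reproduce here. The check is to list when LSR is scored and then trace the baseline rule.

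**1. Scheduled LSR assessments.** Day 1, Weeks 2, 4, 8 and 12: five in all. Pre-dose: 0 of 5. The composite is 6 components scored 0 to 4, so its maximum is 6 × 4 = 24, as SAP 13.2 states.

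**2. The rule applied to a Day 1 LSR taken 30 minutes after dosing.**

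| Situation | Result under SAP 7 and 10.2 | Change and shift tables |
|---|---|---|
| Time not recorded | Assumed pre-dose; becomes baseline | Filled, from a post-dose score |
| Time recorded, definition applied as written | No record precedes first application; baseline missing | Not computable as defined |
| Time recorded, but the SAP 4 wording or the eCRF visit label is taken as an exception | Day 1 score becomes baseline | Filled, from a post-dose score |

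If times are missing for only some subjects and the definition is applied as written, only those subjects get a baseline. The annotated eCRF is cited in SAP 2 but is not among the documents, so which row applies is unknown. No row gives a pre-treatment baseline.

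**3. What a post-dose baseline does.** Change = later score − Day 1 score. The scores below are invented to show the mechanism. They are not estimates.

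- *Immediate reaction that resolves.* Erythema 2 on Day 1, all components 0 at Weeks 2 to 12. Change = 0 − 2 = −2 at each of the four visits, and the shift is 2 to 0. The tables show improvement. The highest score after Day 1 is 0, so the SAP 13.3 LSR criterion is not met. With Day 1 counted, the highest score is 2 and it is met.
- *Immediate reaction that persists.* Erythema 1 at all five assessments, other components 0. Change = 1 − 1 = 0 at each visit, and the shift is 1 to 1. The tables show no change. The criterion is still met, through the later visits.
- *Larger first reaction.* Composite 3 on Day 1 and 2 at Week 2. Change = 2 − 3 = −1. If the unmeasured pre-dose score had been 0, the change would have been 2 − 0 = +2.
- *No immediate reaction.* Day 1 score 0. A post-dose baseline then gives the same change as a pre-dose score of 0 would.

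**4. Who is missed by SAP 13.3.** With all visits attended, a subject drops out of the LSR criterion only if Day 1 is not counted as post-baseline and no component reaches 1 at Weeks 2, 4, 8 or 12. Such a subject may still qualify through an application-site TEAE or a moderate BOTE score.

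**5. Is an LSR exception stated?** None appears in SAP 7, 10.2, 13.2 or 13.3, or among the four changes listed in SAP 14. All three SAP versions in the file carry the same text in 13.2.

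**The case against.** The strongest reply is that the plan does have an LSR baseline. SAP 10.2 allows noted exceptions, SAP 4 describes an LSR at Baseline after dosing, and SAP 7 assigns records by eCRF visit label, where Day 1 is the Baseline visit. On that reading the Day 1 score is the reference whether or not it is timed, and the tables can be filled. This stands in part. A reader might infer that a recorded time makes every planned change and shift result uncomputable; the documents do not establish that. But the reply concedes the main point, because the baseline it offers is still post-dose.

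Second, Day 1 reactions are not hidden. Scores are in Listing 16.2.9.2 and, where Day 1 serves as baseline, the shift table shows them by arm as the starting category. The component table for Weeks 2 to 12 needs no baseline. Clinically significant LSRs are reported as AEs, and TEAEs count from the first application. All of this stands, and it limits the consequences. It does not cover a mild Day 1 reaction that is not judged clinically significant and resolves before Week 2.

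Third, one might find a separate fault in SAP 13.3, whose summary sentence lists "at least 1 moderate BOTE inflammation score, and any LSR component score" of 1 or more without the post-baseline qualifier. That is most likely shorthand: the qualifier is dropped for BOTE too, the preceding sentence has already defined both items, and the next restores it for LSR.

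Fourth, the table shells and analysis dataset specifications are not among the documents and may settle the labelling. That is possible, but the SAP text would still say otherwise.

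**Conclusion.** The point holds. No pre-treatment LSR is scheduled, and SAP 13.2 plans tables that need one. On any reading of SAP 7 and 10.2, the tables either present an on-treatment score as pre-treatment status or cannot be computed as defined. This is a rule that gives a wrong result, not merely a missing detail.

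The reach is limited. Only descriptive safety summaries are affected; the primary and secondary endpoints, alpha and power are not. The size and direction of any distortion are unknown, because the documents give no 30-minute LSR data by arm. A reader might infer that the tables would favour SB206, but the documents do not support a direction. Nor does counting table entries measure bias: 4 composite changes plus 6 × 4 = 24 shift comparisons gives 28 per arm, which says how many results use the baseline, not how far they are off.

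The conclusion rests on the schedule being followed as written, with no LSR recorded before the first application. It should be corrected before unblinding, as a moderate point.

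**What to change.** Change SAP text and table shells only, before unblinding:

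1. In SAP 7 and 10.2, exempt LSR from the rule that treats an untimed same-day record as pre-dose. State that no pre-treatment LSR exists and that Day 1 is the first post-dose assessment.
2. In SAP 13.2, report Day 1 component and composite scores by arm alongside Weeks 2, 4, 8 and 12.
3. Relabel the LSR change and shift tables as from the Day 1 post-dose assessment, or drop them.
4. In SAP 13.3, count Day 1 as a post-dose, on-treatment score in the LSR criterion, with the same wording in each sentence.

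The shells concerned are Tables 14.3.6.1.1 to 14.3.6.1.3 and 14.3.6.2. No new data, visits or protocol amendment are needed. The cost is minor shell editing and possibly a higher reported LSR incidence, because Day 1 reactions would be counted.
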